STUDY SUMMARY

RESEARCH TITLE:

Evaluation of an alternative treatment for localized prostate cancer using MRI-guided transurethral ultrasound with 1-year control for absence of cancer.

Abbreviated Title : MRI-TULSA

Sponsor : Hôpitaux Universitaires de Strasbourg

Principal Investigator: [name] [name]

N° HUS : 7429

N° IDRCB: 2019-A01537-50

Research justification:

Evaluation of a comprehensive alternative prostate treatment for the management of localized prostate cancer.

Primary objective:

Demonstrate that mri-guided transurethral ultrasound (mri-tulsa) enables disease control with absence of clinically significant cancer at the 1-year control biopsy.

Secondary objectives:

1. Evaluate biological response (psa) after treatment.
2. Verify absence of any cancer at 1-year control biopsies.
3. Calculate survival without radical salvage treatment (surgery, radiotherapy, or cryotherapy).
4. Evaluate side effects, complications, and hospitalizations related to device use.
5. Assess satisfactory clinical tolerance post-treatment (urinary functional symptoms, urinary continence, erectile dysfunction, quality of life).

Primary evaluation criterion

Absence of clinically significant cancer at 1-year prostate biopsy.

Clinically significant cancer defined by:

- Gleason ≥ 7, or
- 3 mm cumulative positive biopsy regardless of gleason score, or
- 2 positive biopsies

Critères d'évaluation secondaires :

1. Psa variation between pre- and post-operative periods.
2. Presence of non-clinically and clinically significant cancer at 1-year control biopsies.
3. Absence of salvage treatment.
4. Presence of complications requiring hospitalization.
5. Assessment of functional impact and quality of life:
 - a. Urinary continence (usp)
 - b. Erectile function (iief-15 ≤16)
 - c. Quality of life (eortc qlq-c30)
 - d. Ipss score

Experimental plan

Prospective, monocentric, interventional study on patients.

Inclusion criteria :

- Male ≥50 years, no upper age limit

- Histological proof of prostate adenocarcinoma
- Gleason \leq 7(3+4)
- $<\text{t3}$ clinical, n0, m0
- Psa <15 ng/ml
- Prostate volume < 90 cc
- Ecog performance status 0-1
- Radiological tnm $\text{t}\leq 2$, n0, m0
- First-line treatment or relapse after primary radiotherapy
- Subject affiliated with a social security health insurance regime
- Subject able to understand study objectives and risks and provide informed consent
- Subject informed of pre-study medical visit results

Non-inclusion criteria

- Prostate gland size exceeding 5 cm length and 6 cm axial diameter on reference mri
- Prostate tissue containing cysts and/or calcifications > 1 cm (calcifications or cysts < 1 cm tolerated if not located near the periphery where temperature control occurs)
- Contraindication to mri (e.g., electrical or metallic implants, metallic fragments in body)
- Contraindication to gadolinium contrast (hypersensitivity to gadoteric acid, meglumine, or gadolinium-containing drugs)
- Contraindication to general anesthesia
- Metastatic cancer on imaging
- History of other cancer except non-melanoma tumor effectively treated 2 years prior to inclusion
- Irreversible hemostasis disorders
- Inability to provide informed information (emergency situation, comprehension difficulties)
- Urinary infection on ecbu 10 days before procedure not effectively treated at least 48 hours prior
- Subject under judicial protection
- Subject under guardianship or curatorship
- Subject in exclusion period from previous or ongoing study

Trial procedure

Information visit: consultation in urology surgery department for histologically confirmed localized prostate cancer. Patient informed about study. Pelvic mri and bone scintigraphy performed prior to inclusion in study.

Inclusion visit: informed consent and pre-therapeutic clinical evaluation (usp, ipss, iief-15, eortc qlq-c30).

Anesthesia consultation: approximately 3 weeks before surgery.

Hospitalization: 2-3 days for comprehensive prostate treatment.

Follow-up consultations: clinical and biological follow-up at 15 days, 3 months, 6 months, and 12 months with control mri at 3, 6, and 12 months.

End-of-study visit: 1 year post-treatment with systematic prostate biopsy at 12 months post-treatment and/or if suspicious lesion on mri or psa > nadir+2 ng/ml.

Experimental drug

Not applicable.

Medical device (non-experimental)

Tulsa-pro® is a medical device marketed by profound medical inc., toronto, canada, which obtained its ce (european conformity) marking in january 2018.

This device combines mri imaging with focused transurethral ultrasound treatment of the prostate.

Authorized and/or prohibited treatments

Authorized treatments:

- Usual analgesics levels I to III
- Antiepileptics or antidepressants with marketing authorization for neuropathic pain
- Capsaicin patch for local application
- Gadoteric acid
- Non-adrenaline lidocaine
- Treatments administered for general anesthesia and during post-operative period
- Systematic antibiotic prophylaxis: cefazoline, cefuroxine, gentamicin

Prohibited treatments:

- Anticoagulant treatments constitute a relative contraindication and must be relayed by heparin treatment to allow a therapeutic window (during biopsies and during the therapeutic procedure)
- Radiological procedure, radiotherapy, or prostate cryotherapy during the study period

Antiplatelet agent is not a contraindication; in case of dual Antiplatelet aggregation , a period of 5-10 days of monotherapy should be recommended

Number of subjects required : 25

Statistical method

Statistical analyses will include a descriptive phase and an inferential phase using fully bayesian techniques.

All analyses will be performed using r software.

In the absence of statistical testing, there is no type i error rate to set. Credibility intervals will be symmetric intervals at the 5% level.

Survival analysis without radical salvage treatment will be performed using the kaplan-meier technique.

Provisional timeline

Inclusion period duration: 36 months

Individual subject participation duration: 12 months

Total study duration: 48 months

Exclusion duration:

- During the study: 12 months
- At the end of the study: not applicable
- In case of premature exit: not applicable

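### Men without clinically significant cancer at entry can be enrolled and count as primary successes, and no report of the primary rate by baseline status is planned

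*Combined protocol and SAP*

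**What the plan says.** The Primary objective is stated as: "Demonstrate that mri-guided transurethral ultrasound (mri-tulsa) enables disease control with absence of clinically significant cancer at the 1-year control biopsy". The Primary evaluation criterion is "Absence of clinically significant cancer at 1-year prostate biopsy". Significant cancer has three alternative components: Gleason 7 or more; "3 mm cumulative positive biopsy regardless of gleason score, or" 2 positive biopsies. The criterion is read once, at 1 year, with no reference to the baseline biopsy.

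The Inclusion criteria require "Histological proof of prostate adenocarcinoma". Their other disease limits are all ceilings: Gleason at most 7 (3+4), below T3, N0, M0, PSA below 15 ng/ml. They also admit "First-line treatment or relapse after primary radiotherapy". Nothing in the Non-inclusion criteria removes low-volume Gleason 6 disease.

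The Experimental plan is "Prospective, monocentric, interventional study on patients", with no comparator described. The Statistical method section names a descriptive phase, Bayesian inference, credibility intervals and Kaplan-Meier for salvage-free survival. It states that there is no testing and names no analysis by baseline status. The nearest planned report is the second secondary criterion, "Presence of non-clinically and clinically significant cancer at 1-year control biopsies", which separates the two kinds of cancer at 1 year but not at entry.

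**The concern.** The trial's definition of significant cancer is applied at the end of follow-up but not at the start. A man who meets none of its components at entry can be counted as a success although he had no significant cancer to control. Remaining free of it is a coherent outcome for him, but it does not show that significant cancer was controlled.

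With one arm, no threshold and no test, the estimated rate is the main evidence for the primary objective. If it pools men whose significant cancer disappeared with men who had none, in an unreported ratio, a reader cannot tell which group produced it. What is at stake is the interpretation of the estimate, not a pass/fail decision.

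**Working it through.** **Can such a man be enrolled?** Set the two lists side by side for Gleason 6 in one positive core of under 3 mm:

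| Component of significant cancer | This man at entry | Does eligibility require it? |
|---|---|---|
| Gleason 7 or more | not met | No; Gleason has an upper limit only |
| 3 mm cumulative | not met | No minimum length |
| 2 positive biopsies | not met | No minimum count |

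He has proven adenocarcinoma and no disease criterion excludes him. At 1 year he meets the primary criterion if nothing has changed. This is possible, not certain, because the 1-year biopsy is a new sample.

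**Does another planned report separate him?** Only in part. The any-cancer criterion should count him as a failure if his focus is sampled again, but a small focus can be missed. For relapse patients, the qualifying histology may predate radiotherapy. The listed baseline visits include no biopsy: the text gives "Inclusion visit: informed consent and pre-therapeutic clinical evaluation (usp, ipss, iief-15, eortc qlq-c30") and, before it, pelvic MRI and bone scintigraphy.

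**How large could the effect be?** The plan gives no figure to reproduce: the 25 patients come with no target rate, prior or precision goal. Let f be the share without significant cancer at baseline, q their success rate and s the success rate in the others. Then

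pooled rate = f × q + (1 − f) × s, so pooled rate − s = f × (q − s).

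All three inputs are assumptions. Excess of the pooled rate over s, in percentage points:

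| | f = 10% | f = 20% | f = 40% |
|---|---|---|---|
| s = 60%, q = 90–100% | +3 to +4 | +6 to +8 | +12 to +16 |
| s = 80%, q = 90–100% | +1 to +2 | +2 to +4 | +4 to +8 |
| s = 90%, q = 90–100% | 0 to +1 | 0 to +2 | 0 to +4 |
| s = 60%, q = 80% | +2 | +4 | +8 |
| s = 80%, q = 80% | 0 | 0 | 0 |
| s = 90%, q = 80% | −1 | −2 | −4 |

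For example, 0.40 × (1.00 − 0.60) = 0.16. In patients, 0.16 × 25 = 4 and 0.04 × 25 = 1. The difference is zero if f = 0 or q = s.

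**What would a breakdown show?** Intervals are the 2.5% and 97.5% points of Beta(1 + x, 1 + n − x). The flat prior is assumed, and the plan's 5% level is read as a 95% interval.

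- All patients, 20/25 = 80%: 61–91%, about 30 points wide.
- Five men without baseline significant cancer, all successes: the others are 15/20 = 75%, 53–89%, 36 points wide.
- Ten such men, all successes: the others are 10/15 = 67%, 41–85%, 43 points wide.

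The same 80% can thus stand for 75% or 67% among the men the objective most concerns.

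**The case against.** The strongest reply is that the problem has not been shown to be material. Gleason 3+4 is eligible and is significant at entry, as is Gleason 6 with 2 positive biopsies or 3 mm. Only single-core Gleason 6 under 3 mm escapes. At s = 80% and f = 10–20% the excess is 1–4 points, at most one patient in 25, against an interval about 30 points wide. The 16-point case needs f = 40%, q = 100% and s = 60% together, and the sign can reverse. This stands, and it limits the weight of the point. It does not remove it, because f is unknown and the text does not commit to reporting it.

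Second, the text is a summary, and its descriptive phase could hold a baseline-by-outcome table. That is fair: if the full plan has one, the sponsor need only point to it.

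Third, the objective can be read as disease control in localized cancer generally, for which staying free of significant cancer counts. Success by sampling alone can also occur in men with significant cancer at entry. Both are true. They bear on how the pooled rate is described, not on whether its two parts should be visible.

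Fourth, the radiotherapy point is conjecture, since the text does not date the histology. That is accepted; the main point does not depend on it.

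Last, subset intervals in 25 men are wide: 5/5 gives 54–100%. That calls for cautious reading, and is no reason to leave the mix undisclosed.

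**Conclusion.** The concern holds. On the supplied text, men without significant cancer by the trial's own definition can be enrolled and can count as primary successes with no device effect, and no report of the primary rate by baseline status is planned. A single pooled rate therefore cannot by itself show control of significant cancer in men who had it.

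The size is unknown. Under the assumed ranges with q = 90–100% it runs from 0 to 16 points, often at most one patient in 25, and it is zero or negative if q does not exceed s. No formal decision depends on it. It should be fixed because the remedy is cheap and changes what can be concluded. Confidence is medium, because the document is a summary and the baseline mix is not given.

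**What to change.** Keep the all-patient rate as the primary estimate. Before outcomes are known, classify each patient from existing pathology reports, using the protocol's definition and reading the 3 mm and 2-biopsy components exactly as at 1 year:

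1. **Significant:** Gleason 7, or either other component documented as met, even if other core data are missing.
2. **Not significant:** Gleason 6, with core count and length documented and neither component met.
3. **Unclassified:** any other case. For relapse after radiotherapy, only histology taken after radiotherapy and before study treatment counts; without it the patient is unclassified.

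Pre-specify that the primary proportion and its 95% credible interval are also reported by baseline status, with a sensitivity analysis that counts unclassified men first as significant and then as not. State that any claim of control of significant cancer rests on the men who had it at baseline. The report should add that such men can still fall below the threshold on re-biopsy by sampling alone, so the breakdown reduces this limitation but does not remove it.

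The cost is a short paragraph in the analysis plan and data abstraction. No procedure is added and no patient leaves the primary estimate. The downsides are the wider subset intervals and some unclassified patients. For example, take 20/25 overall, with 5 not significant and 5 unclassified, all successes, and 10/15 among significant men. The sensitivity analysis then runs from 10/15 = 67% (unclassified counted as not significant) to (10 + 5)/(15 + 5) = 15/20 = 75% (counted as significant).

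### Secondary criterion 4 counts only complications that need admission, so it does not measure all that secondary objective 4 sets out to evaluate

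*Combined protocol and SAP*

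**What the plan says.** The secondary objectives and the secondary evaluation criteria are two lists numbered 1 to 5 that run in parallel. Item 4 of the objectives is to "Evaluate side effects, complications, and hospitalizations related to device use". Item 4 of the criteria is "Presence of complications requiring hospitalization". It gives no severity scale, relatedness rule or time window.

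Three parts of the Trial procedure section bear on how criterion 4 would be applied:

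- Every man has a scheduled admission: "Hospitalization: 2-3 days for comprehensive prostate treatment".
- Men are seen again after discharge: "Follow-up consultations: clinical and biological follow-up at 15 days, 3 months, 6 months, and 12 months".
- The protocol adds a further invasive procedure: "systematic prostate biopsy at 12 months post-treatment and/or if suspicious lesion on mri", or on a PSA rise above nadir.

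The Statistical method section says "Statistical analyses will include a descriptive phase and an inferential phase using fully bayesian techniques". It names no safety variable.

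On function, objective 5 is to "Assess satisfactory clinical tolerance post-treatment (urinary functional symptoms, urinary continence, erectile dysfunction, quality of life"). Criterion 5 lists USP, IIEF-15, QLQ-C30 and IPSS. Only erectile function has a threshold (IIEF-15 ≤16, item 5b). The same four instruments are completed at the inclusion visit. Criterion 1, on PSA, is expressly a comparison of before with after treatment; items 5a to 5d carry no such statement.

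**The concern.** An objective is answered only by what its criterion counts. Objective 4 names three kinds of event. Criterion 4 keeps one of them, and only when it is serious enough to need admission. In a single-centre study of 25 men with no comparator described, the tolerability of the device will be judged largely from this rate and the criterion 5 scores. If a man has a device-related complication that is treated as an outpatient and is not a matter of continence, urinary symptoms, erection or quality of life, he appears in neither. The safety result would then look better than the objective warrants.

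Two boundary cases are also left to the reader: admissions that follow a control biopsy, and complications arising during the planned stay. Two careful analysts could report different rates from the same records.

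The lesser concern is that a proportion at or below a fixed IIEF-15 score after treatment does not use the baseline that the plan collects.

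**Working it through.** **No stated figure to reproduce.** The plan gives 25 as the number of subjects, with no target rate, prior or precision behind it, and no safety rate. The check on criterion 4 is a comparison of texts.

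**Step 1. Objective 4 against the criteria, by type of device-related event.**

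| Device-related event | In objective 4? | Counted by a stated criterion? |
|---|---|---|
| Complication leading to readmission | Yes | Yes, criterion 4 |
| Functional or quality-of-life effect, no admission | Yes, as a side effect | Yes, through the criterion 5 scores |
| Other side effect or complication, no admission | Yes | No |
| Complication within, or prolonging, the planned stay | Yes | Unclear |

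The third row is the gap, and it needs no assumption. For device-related events, the men counted by criterion 4 are a subset of the men covered by objective 4. The criterion can therefore only equal or understate the objective, and it understates as soon as one man has nothing but third-row events.

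**Step 2. Boundary cases.** An admission after a control biopsy is a complication of a study procedure but not of device use. Objective 4 is tied to device use; criterion 4 does not repeat the tie. Whether such an admission counts is not stated. For the planned stay, requiring hospitalization could mean readmission, a longer stay, or any complication treated while the man is already in hospital.

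**Step 3. Size per man.** 1/25 = 0.04, so each man classified differently moves the rate by 4 percentage points. The documents give no event rates, so the number of men affected cannot be derived.

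**Step 4. Criterion 5b.** Eligibility sets no erectile-function requirement, has no upper age limit and admits relapse after radiotherapy, so some men may be at or below 16 at inclusion. Suppose ≤16 denotes dysfunction (the plan does not say so), k of 25 men are there at inclusion, none recovers, and x are there after treatment. New onset is then (x − k)/(25 − k). With x = 13, chosen only to show the range:

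- k = 5: 8/20 = 40%
- k = 10: 3/15 = 20%
- k = 13: 0/12 = 0%

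The same post-treatment figure of 13/25 (52%) fits all three.

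**Step 5. Precision of the alternative.** I read "Credibility intervals will be symmetric intervals at the 5% level" as equal-tailed 95%. For a paired mean change, the half-width in units of the SD of the individual changes is t(0.975, n − 1)/√n. This matches the posterior interval under the standard reference prior, which is my assumption, since the plan states no prior.

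- n = 25: 2.064/5 = 0.41 SD
- n = 20 with both assessments: 0.47 SD

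**The case against.** The strongest reply is that the text is headed a study summary. Grading, relatedness and time windows are details a summary may omit, and the clinical visits and the descriptive phase may well lead to wider reporting. That is fair, and it limits the claim: the plan does not say that other events will go unreported. But possible reporting is not a defined criterion, and the criterion that is given covers less than its objective.

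A second reply is that many side effects of this treatment are functional and fall under criterion 5. That stands, and the gap is confined to events outside those domains.

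A reader might go further and infer that criterion 4, having no device-use condition, would count an admission for any unrelated illness. The wording does not support this. It counts complications, not admissions, and an unrelated illness is not ordinarily a complication; read beside its objective, the criterion is about treatment. Only biopsy admissions are really unclear. Nor does the scheduled admission make every man a case. A complication managed inside that stay arguably did not require hospitalization, so what remains is an ambiguity, which alone would be only missing detail.

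On 5b, the heading of criterion 5 speaks of functional impact, and all four instruments are completed before treatment, so a before-and-after reading is natural. Objective 5 can also be read as status after treatment. What is missing is an explicit rule. The meaning of ≤16 is not given either, so the criticism is conditional on its denoting dysfunction.

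**Conclusion.** The point holds. Criterion 4 is narrower than objective 4, and its rate as written understates the device-related events the objective asks about whenever a man has only non-functional events managed without admission. This rests on the wording of the supplied text alone; fuller definitions may exist elsewhere. The treatment of biopsy admissions and planned-stay complications is a secondary ambiguity.

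The size cannot be stated beyond 4 percentage points per man. Any particular contrast between a criterion 4 rate and an objective 4 rate would rest on invented counts.

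On 5b, if ≤16 denotes dysfunction, a post-treatment proportion alone cannot separate existing from new dysfunction.

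Severity is modest: this is a matter of secondary endpoint definition, with no hypothesis test attached. The sponsor should correct it, but the primary criterion and N = 25 do not depend on it.

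**What to change.** **Criterion 4.** Define it as the number of men with at least one adverse event judged related to device use, from treatment to 12 months and including the planned stay, by severity grade on a named scale, recorded at the visits already scheduled. Report readmission or prolongation of the planned stay as a subset. List separately the events attributed to a control biopsy, to other procedures such as anaesthesia, or to other causes. Keeping the relatedness condition to device use matches the objective; extending it to all procedure-related events would widen the objective and should be a declared choice.

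**Criterion 5.** State which IIEF-15 score or domain the value 16 refers to. Report paired change from inclusion to 12 months in men with both assessments, with the number missing, for IIEF-15 and likewise for USP, IPSS and QLQ-C30. Describe it as change after treatment, since no comparator isolates the device effect. New onset among men above the cut-off at inclusion can be a supplementary figure only, because it rests on fewer men.

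**Cost.** No extra visits are needed. Each event needs a relatedness judgement and a grade, and the complication rate will look less favourable than one limited to admissions. The baseline questionnaires are already planned, and criterion 5 cannot be assessed without questionnaires after treatment, so paired change adds little burden beyond making the 12-month collection explicit.

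### Does a fully Bayesian analysis of 25 patients with no named prior leave the primary result open?

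*Combined protocol and SAP*

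**What the plan says.** The primary endpoint is binary for each patient: no clinically significant cancer at the one-year biopsy. No comparator arm is described, so the primary quantity is a single proportion. The Primary objective reads: "Demonstrate that mri-guided transurethral ultrasound (mri-tulsa) enables disease control with absence of clinically significant cancer at the 1-year control biopsy". The sample size line reads "Number of subjects required : 25", with no derivation.

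Under Statistical method, inference is Bayesian ("Statistical analyses will include a descriptive phase and an inferential phase using fully bayesian techniques") and carried out in R. Error control is dealt with in one sentence: "In the absence of statistical testing, there is no type i error rate to set". Interval reporting is given as "Credibility intervals will be symmetric intervals at the 5% level", which I read as 95% equal-tailed intervals. No prior family, parameters, weight or source is given, and no sensitivity prior. The document is headed as a study summary.

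**The concern.** A Bayesian posterior cannot be computed without a prior, and with 25 patients the prior can carry real weight. Silence on the prior also leaves an informative one open. There is a conceivable source for one, since the device was already on the market ("which obtained its ce (european conformity) marking in january 2018"). Such a prior might fit poorly, because eligibility covers two populations, "First-line treatment or relapse after primary radiotherapy", in no stated proportion.

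The objective speaks of demonstrating disease control, yet no posterior threshold is set. If a favourable prior were chosen after the biopsies were read, a disappointing result could be reported as a better one, with an interval that is too narrow and sits too high. The public reader could not tell from this document whether the prior had been fixed in advance.

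**Working it through.** **Inputs.** From the document: n = 25, a binary endpoint and symmetric intervals (read as 95% equal-tailed). The document gives no expected rate, target, precision or dropout, so the figure of 25 can be neither reproduced nor refuted. All priors and success counts below are assumptions.

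**Formulae.** With prior Beta(a, b) and x successes in 25, the posterior is Beta(a + x, b + 25 − x), with mean (a + x)/(a + b + 25). The prior is worth a + b patients, and its share of the information is (a + b)/(a + b + 25). The shift from the raw rate is that share times (prior mean − x/25).

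**Step 1: the ordinary way to fill the gap.** Compare the two usual vague priors.

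| Result | Beta(1,1) | Beta(0.5,0.5) | Difference in means |
|---|---|---|---|
| 15/25 | 16/27 = 59.3% (40.6 to 76.6) | 15.5/26 = 59.6% (40.6 to 77.3) | 0.4 points |
| 20/25 | 21/27 = 77.8% (60.6 to 91.0) | 20.5/26 = 78.8% (61.6 to 91.9) | 1.1 points |
| 23/25 | 24/27 = 88.9% (74.9 to 97.6) | 23.5/26 = 90.4% (76.7 to 98.3) | 1.5 points |

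Differences are taken before rounding. Each is small beside an interval half-width of about 18 points at 15/25.

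**Step 2: the adverse case.** Assume an optimistic prior worth 10 patients (share 10/35 = 29%) or 20 patients (share 20/45 = 44%), and 15/25 observed.

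| Prior | Posterior mean | 95% interval | Shift from Beta(1,1) |
|---|---|---|---|
| Beta(8,2) | 23/35 = 65.7% | 49.5 to 80.3 | +6.5 |
| Beta(9,1) | 24/35 = 68.6% | 52.5 to 82.6 | +9.3 |
| Beta(16,4) | 31/45 = 68.9% | 54.8 to 81.4 | +9.6 |
| Beta(18,2) | 33/45 = 73.3% | 59.7 to 85.0 | +14.1 |

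**Step 3: how far this depends on the assumptions.**
- The same four priors give +9.0 to +18.5 points at 12/25, +3.9 to +9.6 at 18/25, and −0.7 to +3.7 at 22/25.
- A prior worth only 5 patients, with mean 80% or 90%, gives +4.1 or +5.7 at 15/25.
- A sceptical Beta(5,5) gives 20/35 = 57.1% at 15/25, which is −2.1. At 23/25 it gives 28/35 = 80.0%, which is −8.9. The direction is therefore not fixed either.

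**Step 4: interval coverage at a true rate of 60%** (exact binomial sums). Beta(1,1) covers 93.6%, Beta(8,2) 92.5%, Beta(16,4) 84.6% and Beta(18,2) 57.5%. The severe loss comes from the last prior. Under Beta(18,2), the chance of 15 or fewer successes in 25 is 0.9%, so such a result would be an obvious conflict between prior and data.

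**The case for a change.** The strongest case for a change is this. The section finds room for software, error-rate reasoning and interval type, but leaves out the one input without which the posterior cannot be calculated. The same 15/25 could be reported as 59% or 73%, and both would agree with the text. If a vague prior is intended, writing it down costs one sentence; if it is not, prespecification matters a good deal.

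Much of this stands. The prior is absent, the arithmetic is right, and stating a prior before outcomes are known is good practice. Any informative prior would need its source and weight on record.

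What does not stand is the step from silence to a defect. Reaching 73% takes four things together: an informative prior used as primary, a prior mean near 90%, a weight near 20 patients, and about 15 successes. The document suggests none of them. The marketing sentence carries no efficacy data and no hint of borrowing. The gap may also belong to the summary alone, where prior parameters are often left out. Requiring Beta(1,1) as primary, with every informative prior demoted, is a preference on which Bayesians reasonably differ.

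The absent threshold behind the word demonstrate is a separate matter. The section already says that no test is done, so rewording the objective would alter no analysis. Error rates for an invented threshold, or pooled rates for an invented patient mix, measure nothing in this plan.

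**Conclusion.** The concern does not call for a change. The summary omits the prior, but nothing it states is wrong, and analysts would fill the gap sensibly. Between the two usual vague priors the primary estimate moves by 0.4 points at 15/25, 1.1 at 20/25 and 1.5 at 23/25.

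The larger figure, 6.5 to 14.1 points at 15/25, is an illustration and not a bound. It holds only if a prior with mean 80% to 90%, worth 10 to 20 patients, is made primary. Over 12/25 to 18/25 those same priors give about 4 to 19 points, and at 22/25 they give less than 4.

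The conclusion rests on two assumptions: that the primary prior is vague, or is stated in a fuller protocol, and that the intervals are 95% equal-tailed. If an informative prior turned out to be primary with no prior record of its source and weight, the question would have to be reopened.

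### The prohibited list bars two of the three salvage treatments that secondary objective 3 counts as events, and salvage prompted by the 12-month biopsy falls outside the salvage-free survival estimate

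*Combined protocol and SAP*

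**What the plan says.** The third secondary objective is: "Calculate survival without radical salvage treatment (surgery, radiotherapy, or cryotherapy" (closing bracket omitted). The matching secondary criterion is only "Absence of salvage treatment". The Statistical method section assigns the analysis to Kaplan-Meier and adds nothing on time origin, event date or censoring.

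The Authorized and/or prohibited treatments section has a bullet that bars radiological procedures, radiotherapy and prostate cryotherapy for the length of the study. It does not list surgery and carries no exception for a man whose treatment has failed.

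On timing, the Provisional timeline states "Individual subject participation duration: 12 months", with 36 months of inclusion and 48 months in total. The Trial procedure section describes "End-of-study visit: 1 year post-treatment with systematic prostate biopsy at 12 months post-treatment", followed by "and/or if suspicious lesion on mri or psa > nadir+2 ng/ml". Follow-up visits are at 15 days and 3, 6 and 12 months, "with control mri at 3, 6, and 12 months". No visit after month 12 is listed.

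**The concern.** Two features of the plan work against the same endpoint.

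First, the treatment rules and the endpoint definition conflict. A man found to have failed at, say, month 6 might reasonably be offered radiotherapy. Under objective 3 that is an event; under the prohibited list it is not allowed. The text does not say whether he would count as an event, be recorded as a protocol deviation, or leave the study and be censored. If he were censored, the curve would lose the very events it is meant to count. If the list were obeyed, his choice among the three named rescue options would shrink to surgery. That matters for his care as well as for the analysis.

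Second, the one biopsy that every man is scheduled to have takes place as observation closes. It has to be read and discussed before anyone is treated on the strength of it, so salvage that follows from it comes after the estimate has been fixed. A reader who sees a high salvage-free figure beside a primary objective framed as disease control could take it to mean more than it does.

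**Working it through.** **1. Event types against the prohibited list**

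| Salvage type in objective 3 | On the prohibited list? | Salvage exception stated? |
|---|---|---|
| Surgery | No | Not needed |
| Radiotherapy | Yes | No |
| Cryotherapy | Yes (prostate) | No |

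Two of three event types are barred. Events are reduced, not abolished: surgery remains open, and a barred treatment that is given anyway still meets the definition in objective 3.

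**2. Timeline**

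Inclusion 36 months + participation 12 months = 48 months, which reproduces the stated total. For the last man enrolled, 48 − 36 − 12 = 0 months remain after his participation ends. If the 12 months run from inclusion, they end slightly before the biopsy 12 months after treatment, because the anesthesia consultation alone is about 3 weeks before the procedure. On either reading no period is set aside for treatment decided on the biopsy result.

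**3. Routes by which salvage can be seen**

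MRI at 3 and 6 months, and a biopsy for a suspicious lesion or a PSA rise, can find failure early. Salvage that follows is visible if it is delivered before month 12. Salvage that follows the systematic 12-month biopsy is not.

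**4. Illustration only (all inputs assumed)**

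The documents give 25 men and nothing else that bears on size. Assume:

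- *F* = 5 or 8 men fail and eventually have salvage;
- *e* = share found early and treated before month 12 (0, 0.25 or 0.5);
- *s* = share of those who have surgery (0.5 or 1);
- no barred treatment is given, and no man is lost, so Kaplan-Meier at 12 months equals the simple proportion.

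Events seen = *F·e·s*. Unseen = *F*(1 − *e*), due to timing, + *F·e*(1 − *s*), due to the ban. Ban share of unseen = *e*(1 − *s*)/(1 − *e·s*).

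| *e*, *s* | *F* = 5: seen; 12-month figure | *F* = 8: seen; 12-month figure | Ban share of unseen |
|---|---|---|---|
| 0, either | 0; 100% | 0; 100% | 0% |
| 0.25, 0.5 | 0.625; 97.5% | 1; 96% | 14% |
| 0.25, 1 | 1.25; 95% | 2; 92% | 0% |
| 0.5, 0.5 | 1.25; 95% | 2; 92% | 33% |
| 0.5, 1 | 2.5; 90% | 4; 84% | 0% |

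Counting all later salvage gives 1 − 5/25 = 80% or 1 − 8/25 = 68%. The differences run from 90 − 80 = 10 points to 100 − 68 = 32 points. They compare two quantities, salvage by month 12 and salvage at any time, so they do not measure error in the first.

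Flat-prior 95% intervals with 25 men:

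- 0 events, Beta(26, 1): 86.8–99.9%
- 5 events, Beta(21, 6): 60.6–91.0%
- 8 events, Beta(18, 9): 48.2–82.8%

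The interval for the 12-month figure overlaps that for all salvage in 9 of the 10 cells. The exception is *F* = 8 with *e* = 0, where 86.8% lies above 82.8%.

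**The case against.** **The horizon can be inferred.** The title refers to a 1-year control, the end-of-study visit is at 1 year and participation is 12 months. Kaplan-Meier needs no preset landmark, and a 12-month salvage-free figure is a valid result. A reader might contrast criterion 3 with "Absence of clinically significant cancer at 1-year prostate biopsy" and "Presence of non-clinically and clinically significant cancer at 1-year control biopsies", both of which carry a time, and infer that this endpoint has no defined horizon. The documents do not support that. In those two items the time identifies which biopsy is read, and the criteria for PSA, hospitalization and function carry no time either. This objection stands; what remains on timing is a label and the uncaptured salvage.

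**The ban may be meant for concomitant treatment only.** The same bullet bars radiological procedures although MRI is scheduled three times, so a fully literal reading already sits badly with the trial's own schedule. The timeline also foresees premature exit, so a man who fails is not shown to be confined to surgery. This is a fair reading, but it is nowhere written, and a site has only the written rule. The conflict with objective 3 remains.

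**The supplied text is a summary.** Event and censoring rules may be set out more fully elsewhere. That cannot be judged here, and it limits how much weight their absence can bear. It does not explain a prohibition that contradicts an objective within the same summary.

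**The possible misreading is limited.** The primary endpoint and criterion 2 report cancer found at 12 months directly. This stands and keeps the point small.

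**Conclusion.** The point holds in a limited form. Two of the three event types in objective 3 are barred without a salvage exception, so following the list literally leaves only salvage surgery to be given and counted before month 12. Separately, salvage prompted by the systematic 12-month biopsy is not captured.

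Three stronger readings are not supported:

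- *Most salvage goes unseen.* This is an inference. It depends on how many failures are found and treated early, which the documents do not give; at *e* = 0.5 and *s* = 1 exactly half is seen.
- *The estimate is biased by 10 to 32 points.* That range rests wholly on assumed inputs and is the gap between two estimands. With 25 men the intervals would rarely separate them.
- *Salvage events cannot occur.* Surgery is permitted, early detection is possible, and a barred treatment that is given still meets the event definition.

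The size is therefore unknown from the documents. The effect is confined to one secondary endpoint and does not touch the primary conclusion. A correction is still worthwhile because the rule affects rescue care and costs very little to change.

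**What to change.** 1. **Prohibited list and event rule.** Exempt salvage treatment after documented failure from the list. State that any salvage treatment is an event in the salvage-free survival analysis and is not a reason for censoring or withdrawal.
2. **Label and one data item.** Report the Kaplan-Meier result as 12-month salvage-free survival, counted from the treatment date. Once the 12-month biopsy result has been reviewed and a treatment decision made, record whether salvage was decided. Report that count beside the salvage performed, without merging the two. The item should wait for the decision: if it is completed when the pathology result is entered, it may precede the decision and miss the same men.

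The cost is a wording change, a label and one extra data item. No additional patients are needed, and longer follow-up is not required for this correction. The sponsor should expect that the salvage picture may look less favourable once decisions made on the 12-month biopsy are shown.
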